### 7.1.3 3-Month Treatment Visit (Visit 02)

At visit 02, the following investigations will be performed:

- Physical examination including height, weight and pubertal status
- Vital signs (blood pressure and heart rate)
- Blood sampling for anti-hGH antibodies, IGF-I and IGFBP-3 determination
- Concomitant medication recording
- Adverse Events recording
- Fundoscopy, if needed

[REDACTED]

- Drug dispensing, drug accountability and recording

#### **7.1.4 6-Month Treatment Visit (Visit 03)**

At visit 03, the following investigations will be performed:

- Physical examination including height, weight and pubertal status
- Vital signs (blood pressure and heart rate)
- Blood sampling for laboratory testing: Haematology and clinical chemistry including thyroid function, fasting plasma glucose and fasting plasma insulin
- Blood sampling for anti-hGH antibodies, IGF-I and IGFBP-3 determination
- OGTT
- Urinary analysis (dip stick)
- Pregnancy test (only in female patients after onset of menarche)
- Concomitant medication recording
- Adverse Events recording
- Fundoscopy, if needed
- Drug dispensing, drug accountability and recording

#### **7.1.5 9-Month Treatment Visit (Visit 04)**

At visit 04, the following investigations will be performed:

- Physical examination including height, weight and pubertal status
- Vital signs (blood pressure and heart rate)
- Blood sampling for anti-hGH antibodies, IGF-I and IGFBP-3 determination
- Concomitant medication recording
- Adverse Events recording
- Fundoscopy, if needed
- Drug dispensing, drug accountability and recording

#### **7.1.6 12-Month Treatment Visit (Visit 05)**

At visit 05, the following investigations will be performed:

- Physical examination including height, weight and pubertal status
- Vital signs (blood pressure and heart rate)
- Blood sampling for laboratory testing: Haematology and clinical chemistry including thyroid function, fasting plasma glucose and fasting plasma insulin
- Blood sampling for anti-hGH antibodies, IGF-I and IGFBP-3 determination
- OGTT
- Urinary analysis (dip stick)
- Pregnancy test (only in female patients after onset of menarche)

- Concomitant medication recording
- Adverse Events recording
- Fundoscopy, if needed
- Drug dispensing, drug accountability and recording

#### **7.1.7 15-Month Treatment Visit (Visit 06)**

At visit 06, the following investigations will be performed:

- Physical examination including height, weight and pubertal status
- Vital signs (blood pressure and heart rate)
- Concomitant medication recording
- Adverse Events recording
- Fundoscopy, if needed
- Drug dispensing, drug accountability and recording

#### **7.1.8 18-Month Treatment Visit (Visit 07)**

At visit 07, the following investigations will be performed:

- Physical examination including height, weight and pubertal status
- Vital signs (blood pressure and heart rate)
- Blood sampling for anti-hGH antibodies, IGF-I and IGFBP-3 determination
- Concomitant medication recording
- Adverse Events recording
- Fundoscopy, if needed
- Drug dispensing, drug accountability and recording

#### **7.1.9 21-Month Treatment Visit (Visit 08)**

At visit 08, the following investigations will be performed:

- Physical examination including height, weight and pubertal status
- Vital signs (blood pressure and heart rate)
- Concomitant medication recording
- Adverse Events recording
- Fundoscopy, if needed
- Drug dispensing, drug accountability and recording

#### **7.1.10 24-Month Treatment Visit (Visit 09) and subsequent visits performed annually (Visit 11, Visit 13 etc)**

The following investigations will be performed:

- Physical examination including height, weight and pubertal status
- Vital signs (blood pressure and heart rate)
- Blood sampling for laboratory testing: Haematology and clinical chemistry including thyroid function, fasting plasma glucose and fasting plasma insulin
- Blood sampling for anti-hGH antibodies, IGF-I and IGFBP-3 determination
- OGTT
- Urinary analysis (dip stick)
- Pregnancy test (only in female patients after onset of menarche)
- [REDACTED]
- Concomitant medication recording
- Adverse Events recording
- Fundoscopy, if needed
- Drug dispensing, drug accountability and recording

#### **7.1.11 30-Month Treatment Visit (Visit 10) and subsequent visits performed annually (Visit 12, Visit 14 etc)**

The following investigations will be performed:

- Physical examination including height, weight and pubertal status
- Vital signs (blood pressure and heart rate)
- Blood sampling for IGF-I and IGFBP-3 determination
- Concomitant medication recording
- Adverse Events recording
- Fundoscopy, if needed
- Drug dispensing, drug accountability and recording

#### **7.1.12 Final Visit of treatment period**

At final visit of treatment period, the following investigations will be performed:

- Physical examination including height, weight and pubertal status
- Vital signs (blood pressure and heart rate)
- Blood sampling for laboratory testing: Haematology and clinical chemistry including thyroid function, fasting plasma glucose and fasting plasma insulin
- Blood sampling for anti-hGH antibodies, IGF-I and IGFBP-3 determination
- OGTT
- Urinary analysis (dip stick)
- Pregnancy test (only in female patients after onset of menarche)

[REDACTED]

- Concomitant medication recording
- Adverse Events recording
- Fundoscopy, if needed
- Drug accountability and recording

## **7.2 Treatment exposure and compliance**

Patient compliance will be assessed by the collection of used, partly used and unused vials as well as cartridges at each visit. The number of returned vials and the quantity of unused treatment remaining in the vials will provide information on treatment compliance, which will be recorded in the source document at each visit. Patients must comply with the dose schedule. The daily dose should be maintained in the range between 80% and 120% of the recommended daily dose of 0.035 mg/kg BW depending on the patient's responsiveness.

## **7.3 Efficacy**

### **7.3.1 Methods and timing for assessing, recording and analysis of efficacy parameters**

At each visit, which should take place preferably in the morning, patient's height and weight will be assessed and noted.

### **7.3.2 Anthropometric Measurements**

Height measurements will be performed using a wall-mounted stadiometer. Whenever possible, a patient will be measured at each visit at a similar daytime by the same trained person to minimise observer bias. The technique as described by [Tanner et al \(1966\)](#) should be used.

### **7.3.3 Presentation and Calculation of Auxological Data**

Height velocity (HV) will be calculated in cm/year as the difference between two height measurements divided by the time interval in days between these two measurements multiplied by 365.25.

Height and height velocity will not only be expressed in cm and cm/year, respectively, but also in Standard Deviation Scores (SDS), the relative deviation from the mean value of normally growing children of same sex and chronological age or bone age. The SDS values for height and HV will be calculated according to the following formula  $SDS = (X1 - X2) / SD$ , where X1 means the measured value, X2 the mean value for the relevant chronological age (or bone age, where appropriate), and SD stands for the standard deviation for the mean of relevant age. For the calculation of HVSDS, the mean between the CA at the two height measurements should be considered as the relevant CA.

Since the formula for the calculation of SDS is not common practice in all countries (especially for the calculation of height SDS) the inclusion of a patient is evaluated according

to national common practice. The following formula is widely used and allowed for inclusion instead of the formula used for the statistical analysis of the study cited above:

$$SDS = \frac{\text{measured value} - \text{median}}{0.5 * (\text{median} - \text{3rd percentile})}$$

All standardized controlled procedures and methods applied for the calculation of auxological data (with reference to Inclusion Criteria No. 2, 3 and 5) to ensure a common basis and comparability of data derived from the different countries will be filed in the Trial Master File and described in the Clinical Study Report.

### 7.3.4 Weight measurements

Weight will be measured according to the usual clinical practice.

## 7.4 Safety

### 7.4.1 Carbohydrate metabolism

Fasting plasma glucose and insulin levels will be measured at baseline, at 6 and 12 months, then annually during GH treatment, and at the end of treatment.

After an overnight fast, venous blood samples will be taken to assess fasting glucose and insulin levels. Insulin resistance will be estimated using both the homeostasis model assessment (HOMA) (Matthews et al 1985) and quantitative insulin sensitivity check index (QUICKI) (Katz et al 2000, WHO 2002).

$$\text{HOMA} = \frac{\text{fasting insulin } (\mu\text{U/ml}) \times \text{fasting glucose } (\text{mg/dl})}{405 *}$$

\*use constant 22.5 instead of 405 if glucose concentration is reported in mmol/L

$$\text{QUICKI} = \frac{1}{\log \text{fasting insulin } (\mu\text{U/ml}) + \log \text{fasting glucose } (\text{mg/dl})}$$

Glycosylated haemoglobin (HbA1C) will be measured at baseline, at 6 and 12 months and then annually during GH treatment, and at the end of treatment.

An oral glucose tolerance test (OGTT) will be performed at baseline, at 6 and 12 months and then annually during GH treatment, and at the end of treatment.

The OGTT is a provocation test to examine the efficiency of the body to metabolise glucose. The OGTT provides information on latent diabetes states. The OGTT will be carried out according to WHO criteria (2002). After 3 days of an unrestricted, carbohydrate-rich diet, and after overnight fasting, 1.75 grams of glucose per kg body weight (up to a maximum of 75 g) will be administered orally after being dissolved in 250-300 ml of water. Blood samples will be taken 10 minutes before, and 120 minutes after the glucose load. Diabetes mellitus is defined by  $\geq 200$  mg/dl or  $\geq 11.1$  mmol/L blood glucose after 120 minutes.

#### **7.4.2 Immunogenicity**

Subjects will be screened for anti-rhGH antibodies (ABs) at baseline, at 3, 6, 9, 12, 18 and 24 months, then annually during GH treatment and at the end of treatment. Antibody-induced lack or loss of efficacy will be examined by comparing height outcome data between antibody-positive and antibody-negative subjects.

#### **7.4.3 Fundoscopy**

Fundoscopy will be performed only if intracranial hypertension is suspected (severe or recurrent headache, visual problems, nausea and/or vomiting).

#### **7.4.4 Physical examination**

Patients will undergo a general physical examination and will also be questioned about and examined for any local or systemic adverse events. At each scheduled visit during treatment a thorough physical examination including of the following will be made: head (external), eyes, ears, nose and throat, lungs, cardiovascular system, abdomen, musculoskeletal system, skin, lymph nodes, central nervous system and, where appropriate, others. Prepubertal or pubertal status should be assessed by the investigator and expressed in stages as described by [Tanner and Whitehouse \(1976\)](#).

#### **7.4.5 Vital signs**

Vital signs (blood pressure and pulse rate) will be recorded at each visit during treatment in a standardised manner, i.e., after the patient has rested for five minutes in the sitting position.

#### **7.4.6 Laboratory evaluations**

##### **7.4.6.1 Local Laboratories**

Local laboratories will be responsible for performing blood serum and urine determinations; clinical chemistry and complete blood count (CBC) (automated 5-part differential recommended), absolute neutrophil count (ANC) and platelet counts.

All supernatants of samples are destroyed after analysis.

The following laboratory safety tests will be performed at baseline, at 6 and 12 months and annually thereafter for the remainder of GH treatment, and at the end of treatment, unless more frequent assessment is clinically indicated.

Haematology: Haemoglobin, haematocrit, white blood cell count (total and differential) (WBC), red blood cell count (RBC), platelet count, mean cell volume (MCV), mean cell haemoglobin (MCH), mean cell haemoglobin concentration (MCHC), HbA1C, erythrocyte sedimentation rate (ESR).

Biochemistry: Creatinine, urea, aspartate aminotransferase (SGOT/AST), alanine aminotransferase (SGPT/ALT), gamma-glutamyltransferase (gamma-GT), alkaline phosphatase, total bilirubin, albumin, total protein, HDL, LDL, sodium, potassium, chloride, glucose\*, insulin\*, uric acid, total cholesterol\*, triglycerides\*, calcium, phosphorus.

Thyroid function: Free thyroxine (fT4) and thyroid stimulating hormone (TSH).

Urinalysis: pH, glucose, ketones, bilirubin, protein. Pregnancy test only in girls after onset of menarche.

\*fasting serum levels; fasting is defined as no caloric intake for at least 8h

#### **7.4.6.2 Central Laboratory**

Central laboratory will process samples for antibody analysis, IGF-I and IGFBP-3. Instructions on preparation and shipment of samples will be provided in the corresponding Manual. Serum samples stored deep frozen at -70°C for central determination of IGF-I, IGFBP-3 and anti-hGH antibodies. For central laboratory details please refer to lab manual.

##### **7.4.6.2.1 Anti-hGH antibodies**

Anti-hGH antibodies serum levels will be assessed at baseline, at 3, 6, 9, 12, 18 and 24 months, then annually during treatment, and at the end of treatment.

Samples will be stored by the sponsor according currently applicable guidelines in order to potentially re-analyze anti-hGH antibodies at a later stage, if needed.

##### **7.4.6.2.2 IGF-I and IGFBP-3 serum levels**

IGF-I and IGFBP-3 serum levels will be assessed at baseline, at 3, 6, 9 and 12 months, then every 6 months during treatment, and at the end of treatment. All supernatants of samples are destroyed after analysis.

#### **7.4.7 Adverse events**

The investigator has the responsibility for managing the safety of individual subject and identifying adverse events.

An adverse event (AE) is any untoward medical occurrence (e.g., any unfavorable and unintended sign, including abnormal laboratory findings, symptom or disease) in a subject after providing written informed consent for participation in the study until the end of study visit. Therefore, an AE may or may not be temporally or causally associated with the use of a investigational medicinal product.

In addition, all reports of intentional misuse and abuse of the product are also considered an adverse event irrespective if a clinical event has occurred.

The occurrence of adverse events should be sought by non-directive questioning of the subject at each visit during the study. Adverse events also may be identified when they are volunteered by the subject during or between visits or through physical examination, laboratory test, or other assessments.

Abnormal laboratory values or test results constitute adverse events only if they fulfill at least one of the following criteria:

- they induce clinical signs or symptoms,
- the investigator considers them to be clinically relevant,
- they require therapy.

Clinically relevant abnormal laboratory values or test results should be identified through a review of values outside of normal ranges/clinically notable ranges, relevant changes from baseline or the previous visit, or values which are considered to be non-typical in subject with underlying disease.

Adverse events must be recorded on the adverse events CRF with the following information within 10 days of learning of its occurrence (if the event is serious (refer to Section 7.4.8) it must be recorded in the CRF within 24 hours of learning of its occurrence):

- the severity grade (indicating most severe grade during the course of the adverse event)
  - mild: usually transient in nature and generally not interfering with normal activities
  - moderate: sufficiently discomforting to interfere with normal activities
  - severe: prevents normal activities
- its relationship to the study drug(s) (suspected/not suspected)
  - Not suspected: The temporal relationship of the clinical event to trial drug administration makes a causal relationship unlikely, or other drugs, therapeutic interventions or underlying conditions provide a sufficient explanation for the observed event.
  - Suspected: The temporal relationship of the clinical event to trial drug administration makes a causal relationship possible, and other drugs, therapeutic interventions or underlying conditions do not provide a sufficient explanation for the observed event.
  - If the event is due to lack of efficacy or progression of underlying illness (i.e. progression of the study indication) the assessment of causality will usually be 'Not suspected'. The rationale for this guidance is as follows:
    - the symptoms of a lack of efficacy or progression of underlying illness are not caused by the trial drug, they happen in spite of its administration
    - both lack of efficacy and progression of underlying disease can only be evaluated meaningfully by an analysis of cohorts, not on a single subject
- its duration (start and end dates) or 'ongoing' at the 30 day safety follow-up /end of study visit
- whether it constitutes a serious adverse event (SAE) (see Section 7.4.8 for the definition of SAE)

**Unlike routine safety assessments, SAEs are monitored continuously and have special reporting requirements; see Section 8.1**

- action taken: All adverse events must be treated appropriately. Treatment may include one or more of the following: no action taken (i.e. further observation only); study drug dosage adjusted/temporarily interrupted; study drug permanently discontinued due to this adverse event; concomitant medication given; non-drug therapy given, subject hospitalized/subject's hospitalization prolonged.
- Its outcome (not recovered/not resolved; recovered/resolved; recovering/resolving, recovered/resolved with sequelae; fatal; or unknown)

Once an adverse event is identified, it must be followed until its resolution or until it is judged to be permanent, and assessment must be made at each visit (or more frequently, if necessary) of any changes in severity, the suspected relationship to the study drug, the interventions required to treat it, and the outcome.

Information about common side effects already known about the investigational drug can be found in the Investigator Brochure (IB). This information will be included in the subject informed consent form and must be discussed with the subject during the study as needed. Any new information regarding the safety profile of the medicinal product that is identified between IB updates will be communicated as appropriate, for example, via an Investigator Notification or an Aggregate Safety Finding report. New information might require an update to the informed consent form and has then to be discussed with the subject.

The investigator must also instruct each subject to report any new adverse event (beyond the protocol observation period) that the subject, or the subject's personal physician, believes might reasonably be related to study treatment. This information must be recorded in the investigator's source documents, however, if the AE meets the criteria of an SAE, it must be reported to the sponsor.

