### **6.5.9 Study drug discontinuation**

Treatment can be terminated at any time, at the discretion of the investigator or the Sponsor, or at the patient's request, in the event of an AE or due to treatment failure.

Study drug treatment has to be discontinued in the following cases during treatment period:

- Occurrence of overt diabetes mellitus; defined as fasting blood glucose  $\geq 126$  mg/dl or  $\geq 7.0$  mmol/l and abnormal findings in OGTT defined by  $\geq 200$  mg/dl or  $\geq 11.1$  mmol/l after 120 minutes. For further instruction see appendix
- Requirement of an increase of the recommended dose to obtain increased growth velocity
- Renal transplantation
- Diagnosis of benign intracranial hypertension
- Malignancy
- Pregnancy
- Withdrawal of informed consent
- Treatment failure

Treatment failure is defined as: Inadequate response to treatment, e.g. height velocity standard deviation score (HVSDS) below +1 in the first year.

Furthermore a standardized controlled procedure for the calculation of the treatment response (via "Treatment Response Control Fax") was implemented (see also 6.5.3 treatment duration) to ensure a unified flawless computation and to authorize treatment continuation, if applicable (managed by Data Management at Metronomia). In case the Investigator does not agree with the assessment by Data Management, Sandoz is informed and initiates the re-assessment of the treatment response data via an independent specialist reader.

Patients who are withdrawn from the study before completing at least one year of treatment with Omnitrope® will be replaced.

Study drug must be discontinued if the investigator concludes that continuation would result in significant safety risk for that patient and in the event of pregnancy.

Patients who discontinue study drug before completing the study should not be considered withdrawn from the study and should be scheduled for a final visit as soon as possible, at which time all of the assessments for the final visit will be performed.

A Study Drug Discontinuation form should be completed, giving the date and reason for stopping the study drug. All patients who discontinue study drug, including those who refuse to return for a final visit, will be contacted for safety evaluations during the 4 weeks following the last dose of the study drug.

Patients who discontinued this study for any reason will not be able to re-enter the study.

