# **8 Safety monitoring**

## **8.1 Serious adverse event reporting**

To ensure subject safety, the investigator has to report every SAE, regardless of suspected causality, occurring after the subject has provided informed consent and until 30 days after following the last administration of study treatment must be reported to the sponsor (or designated CRO) within 24 hours of learning of its occurrence using the SAE reporting form, and recorded in the CRF.

Any SAEs experienced after this 30 day period should only be reported to the sponsor (or designated CRO) if the investigator suspects a causal relationship to the study drug.

All follow-up information for the SAE including information on complications, progression of the initial SAE and recurrent episodes must be reported as follow-up to the original episode within 24 hours of the investigator receiving the follow-up information. Likewise, queries issued by the sponsor regarding the SAE must be responded to within 24 hours.

An SAE that is considered completely unrelated to a previously reported one must be reported separately as a new event.

Information about all SAEs is collected and recorded on the Serious Adverse Event Report Form. The investigator must assess the relationship to study drug, complete the SAE Report Form in English, and send the completed, signed form within 24 hours to the sponsor. The contact details for SAE reporting are listed in the investigator folder provided to each site.

The original copy of the SAE Report Form and the fax confirmation sheet must be kept at the study site.

Follow-up information must be provided using a new SAE Report Form stating that this is a follow-up to the previously reported SAE. The follow-up information must describe whether the event has resolved or continues, if and how it was treated, whether the blind was broken or not, and whether the subject continued or withdrew from study participation. Each re-occurrence, complication, or progression of the original event must be reported as a follow-up to that event regardless of when it occurs.

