##### **4.6.2.1 Adverse events**

Adverse events (AEs) are to be recorded during the whole study period.

AEs are coded according to Novartis MedDRA, Version 24.1.

The AE data will be listed, sorted by site code, patient number, and preferred term. This list will include: adverse event, MedDRA system organ class, MedDRA preferred term, start date, stop date, intensity, outcome, relationship to study drug, action taken, and a variable indicating whether an AE was considered a serious adverse event (SAE).

AEs starting prior to start of treatment will not be included in the summary tables, but listed only.

A general summary table of AEs will contain the total number of AEs, the total number of SAEs, and separate descriptions of the splits for the variables relationship to study drug, action taken,

outcome and intensity. Outcome is categorized according to the CRF as “resolved” (i.e. resolved completely or resolved with sequelae), “ongoing”, “fatal” or “unknown”.

The incidence of an AE is defined as the number of patients who experience that event, divided by the number of patients in the SAF population. With AE incidence, each event will be counted only once for a given patient. More specifically, if a patient reports the same event more than once, as determined by preferred term and system organ class, that patient will be counted only once for the incidence of the AE. For example, when a patient reported three instances of headache, this patient counts only once towards the total incidence of headache. Incidence of events within a system organ class is defined similarly. Whenever incidence is cross-tabulated with intensity in the summary tables, the incidence of an AE will be calculated for each level of intensity, i.e., the number of patients who experience that AE on a certain level of intensity.

Incidence tables will provide information about rates of AEs per patient-year, calculated as  $\{(number\ of\ patients\ who\ experience\ that\ event)\ / (years\ of\ exposure)\}$ . Additional tables will enable a direct comparison of formulation specific rates of events per patient year.

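### The end of post-treatment safety collection is stated inconsistently (an undefined end of study visit, 4 weeks, 30 days), and the SAP has no onset cut-off after the last dose to match its treatment-time denominator

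*Protocol*

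**What the plan says.** Four statements in the protocol bear on when safety collection ends.

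- The AE definition in 7.4.7 covers occurrences "in a subject after providing written informed consent for participation in the study until the end of study visit". The protocol does not say which visit this is.
- The AE form item in the same section records an event's duration "or 'ongoing' at the 30 day safety follow-up /end of study visit".
- Section 6.5.9 says that all patients who discontinue study drug, including those who refuse a final visit, "will be contacted for safety evaluations during the 4 weeks following the last dose of the study drug". It also asks that the final visit of an early discontinuer take place as soon as possible.
- Section 8.1 says that every SAE from consent "until 30 days after following the last administration of study treatment must be reported to the sponsor", whatever its suspected cause. Later SAEs are reported only on suspicion of a causal link.

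Section 7.4.8 defines an SAE as a kind of adverse event, so it takes over whatever limit the AE definition carries. The flow chart and 7.1 both stop at the Final visit.

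SAP 4.6.2.1 says that AEs are recorded throughout the study and gives one onset rule for the tables: "AEs starting prior to start of treatment will not be included in the summary tables, but listed only". It has no rule for onset after the last dose. SAP 4.4 and the footnotes to the AE table shells define patient-years as treatment time.

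**The concern.** A site cannot tell from these sections when to stop recording. Take a child who stops early, attends the Final visit promptly and is then contacted within 4 weeks. If the Final visit is the end of study visit, a non-serious event that began in between is not an AE by definition. Section 7.4.7 sends later events that are believed related to source documents, and to the sponsor only if serious, so the non-serious event has no clear route to the CRF. A child who refuses the Final visit has no usable end to AE collection at all. An SAE on day 29 or 30 must be reported, but the planned contact may already have taken place.

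The analysis inherits the problem. A post-treatment event that is recorded enters the numerator of a rate whose denominator stopped at the last dose. AE incidence is a secondary objective of a pharmacovigilance study, so the tables should rest on a stated window.

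**Working it through.** **Closing points.** The four statements give three distinct ends: the end of study visit (no number of days), 4 weeks (28 days) and 30 days. The AE form item joins the first and the third with a slash. A longer window for SAEs than for AEs is not in itself a contradiction. The difficulty is that the AE end is undefined and that SAEs are defined through it.

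**Schedule.** The last column of the flow chart and the last item of 7.1 (7.1.12) are the Final visit. Neither shows a 30-day follow-up or a 4-week contact. No interval from last dose to Final visit is given.

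**Part of each window outside the AE definition.** Days outside = window end − day of Final visit, counted from the last dose.

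- Final visit on day 0: 30 − 0 = 30 days of the SAE window and 28 − 0 = 28 days of the contact period.
- Final visit on day 21 (an assumed upper end; the flow chart allows 3 weeks either side of the End visit): 30 − 21 = 9 days and 28 − 21 = 7 days.
- End of study visit read as the 30-day follow-up: 0 days.

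Whatever the reading, a contact made by day 28 leaves at least 30 − 28 = 2 days of the SAE window without an active enquiry.

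**In person-years.** N = 277, from the shell of SAP Table 14.3-1.1. Person-years = 277 × days / 365.25.

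- 30-day window: 277 × 30 / 365.25 = 22.8 (day 0), and 277 × 9 / 365.25 = 6.8 (day 21).
- 28-day period, if every child were contacted: 277 × 28 / 365.25 = 21.2, and 277 × 7 / 365.25 = 5.3.

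**Effect on the rates.** Assume that every event in the 30 days is recorded and that events occur at the same rate off drug as on it. The rate is then inflated by (30 / 365.25) / mean exposure in years = 0.0821 / mean exposure. The documents give no mean exposure. At an assumed 3, 5 or 8 years the inflation is 2.7%, 1.6% or 1.0%.

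**Who can still be reached.** The Study status section of the protocol gives 278 enrolled and 32 on treatment at 31 December 2019. So 278 − 32 = 246 (246 / 278 = 88%) had already stopped, and their first 30 days off drug can no longer be covered by a new contact, except for any who had stopped within the preceding month.

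**The case against.** The slash in the AE form item can be read as naming one event, so that the end of study visit is the 30-day follow-up and the gap in the definition is zero. Other provisions also limit the loss. Section 7.4.7 has each subject told to report later events believed related, and identified AEs are followed to resolution or permanence. Section 8.1 keeps reporting of suspected SAEs open-ended. The numerical effect on descriptive rates is small. All of this stands, and it makes the exclusion of non-serious events conditional. It does not supply the missing definition, put the follow-up in the schedule, or give the SAP a cut-off.

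A reader might infer that completers get no contact while early discontinuers do. The text does not settle this. Section 6.5.9 speaks of all who discontinue drug, and the synopsis uses the same verb for height velocity below 2 cm/year, which section 4 ties to final height. Section 4 also speaks of being discontinued earlier for other reasons, which points the other way.

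A reader might go on to say that AE rates of completers and discontinuers are not comparable. The SAP plans no such comparison: its completer split (2.7 and 4.6.1) is for efficacy only.

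Nor does the metabolic background in Protocol 1.2.4 support the point. It gives impaired glucose tolerance in 8% before treatment, 4% after 6 years and 10% after stopping, the last by OGTT 6 months later. A contact at 30 days would not detect this, and the primary objective is limited to the treatment period.

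**Conclusion.** The inconsistency is real and worth correcting, but its effect is modest. The protocol gives three different ends to post-treatment collection, leaves one undefined and schedules neither follow-up. That non-serious events fall outside the AE definition holds only if the end of study visit is the Final visit, and only for events that begin after it. SAEs have a uniform written 30-day rule, but a contact within 4 weeks cannot cover all of it. The 22.8 person-years is an upper bound that takes the Final visit on the day of the last dose for all 277 children. It falls to 6.8 at an assumed day 21, and the gap is zero if the visit is the 30-day follow-up. The mismatch in the SAP stands on any reading, because it lies in having no post-dose onset rule beside a treatment-time denominator. A count of events lost or misplaced cannot be given, since the documents contain no AE rate.

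**What to change.** **Protocol.** Define the end of study visit. Reconcile 6.5.9, 7.4.7 and 8.1 to one stated window in days from the last dose. Show the contact already provided in 6.5.9 in the flow chart, at the end of that window, for every child still on treatment, including those who stop at final height.

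**SAP 4.6.2.1.** Base the per-patient-year rates on AEs with onset from first to last dose, using the same last-dose date as the exposure calculation in SAP 4.4. Tabulate or list events with later onset separately. Do not add 30 days of person-time for children whose post-treatment window was not actively covered. For most of the 246 already off treatment at the end of 2019 no new contact can cover that window, non-serious events may not have been sought in it, and the extra time would dilute the rates.

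**Cost.** Wording in three protocol sections, one flow-chart entry, one SAP rule with an onset-date filter, and one contact per child still on treatment (32 at 31 December 2019). A few more non-serious events may need recording.
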